# **Table 2. Study Outcome Measures**

Test	Screen ing	Baseline	Daily Study Session s (1-20)	Mid- study	Daily Study Sessions (21-40)	Study End (Follow- up)	Online/ Telephone Survey (Study end date + 1 month)
Medical Clearance	Х						
Expanded Disability Status Scale	X						
Wide Range Achievement Test (WRAT-4)	X	X				X	
Symbol Digit Modalities Test (SDMT)	X	X		X		X	
Beck Depression Inventory-Fast Screen*		Х				X	
tDCS Aptitude Test		X				Х	
tDCS Tolerance Test (2.0 mA, will possibility to repeat at 1.5 mA)		X				Х	
Multiple Sclerosis Neuropsychological Questionnaire (MSNQ)*		Х		X		Х	X
PROMIS Measure of Fatigue, Mood and Health- Related Quality of Life*		X		Х		Х	X
Neuro-Quality of Life*		X		Х		X	X
Fatigue Impact Scale*		Х		Х		X	Х
Fatigue Severity Scale*		Х		Х		X	Х
Pittsburgh Fatigability Scale*		Х		X		X	
Attention Network Test- Interaction*		Х		X		X	
Cogstate Brief Battery*		Х		Х		Х	
ERTSLab Processing Battery*		Х		X		Х	
Controlled Oral Word Association*		X		Х		Х	
Rey Auditory Verbal Learning Test*		X		X		X	X (delayed recall only)
Brief Visuospatial Memory Test- Revised*		Х		Х		Х	
King Devick Test*		Χ		Χ		Х	
Test of Everyday Cognitive Ability*		X		X		X	
Grip Strength*		Х		Х		Х	
Grooved Pegboard*		Х		Х		Х	
Positive and Negative Affect Scale (PANAS)*		Х	Х	Х	Х	Х	
Visual analog scale for		Х	X	Х	X	X	

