# V. DESCRIPTION OF THE PROTOCOL

# The goal of this pilot study is to establish a structured protocol for safe remotely-supervised delivery of 40 consecutive tDCS sessions (active and control conditions) to be used in a randomized, controlled double-blind clinical studies in participants with MS.

*a)* Study Design: Participants will complete a total of 40 sessions across eight weeks: training at baseline with a study technician and then monitoring (through secure online video) by the study technician for the remaining thirty-nine sessions. We will use the most common montage of bilateral dorsolateral prefrontal cortex (DLFPC) placement, with the anodal electrode placed on the left side. This offers ease of reliable electrode placement and wide therapeutic applications. Dose will be up to the target of 2.5 mA with reduction to 2.0, 1.5, or 1.0 mA based on tolerability testing at baseline. At study end, participants in the sham condition will be offered 10 open label active sessions.

**b)** Study Equipment: For the remotely-supervised sessions, participants will be given the speciallydesigned tDCS device and headset, study laptop computer for secure video monitoring with study technician (must have internet access), a detailed reference manual, and a training video. The Soterix mini-CT is uniquely designed for remotely-supervised delivery and requires a one-time use code provided by the study technician to unlock the device for one stimulation session. The device will not operate without correct headset placement and has a single-button option to abort the session. The device will also automatically abort the session if optimal conditions are not maintained. It reports and records a completion code for each session.

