#### **Baseline Visit**:

#### \*Note clinician assessment for medical clearance may occur either before or at the baseline visit

All women who are of child-bearing age will complete a pregnancy test (human chorionic gonadotrophin urine assay) to assure they are eligible for all study procedures. Women who receive a result denoting heightened hCG levels will be considered study screen failures.

Prior to tDCS training, the tests and evaluations detailed in Table 2 will be administered.

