#### tDCS aptitude screen and tolerability test:

• **tDCS Aptitude**: Participants will first complete an aptitude test to confirm that they have the cognitive and motor skills required for headset placement. With instruction of the study technician, they will be asked to insert the sponges onto the headset and place the electrodes into the sponges. The technician will determine whether or not the participant is qualified to proceed. Participants will not be allowed to proceed if they are not able to correctly either 1) attach sponges to headset or 2) place electrodes into the sponges.

**tDCS Tolerability:** The study technician will next directly place the headset and then initiate a one-minute test session, with 30 seconds of ramp-up to target, followed by a 30-second ramp down. The tolerability test will first take place using 2.5 mA stimulation. If the participant tolerates and agrees, 2.5 mA will be used for all following stimulation sessions. Alternatively, if the participant cannot tolerate 2.5 mA, stimulation will be based on highest amplitude tolerated, following 0.5 mA decrements (2.0, 1.5., and 1.0 mA.) till finally a base 1.0 mA stimulation is offered. Once the tolerable dose is established, it will remain constant throughout the study. If the participant cannot tolerate any of the offered stimulation levels, they are excluded from the study.

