#### **Methods and Procedures**

Will mirror the exact methods detailed in section **VI**, with the exception that this study will be an open label feasibility study, with all participants receiving active, open-label tDCS. The exploratory aim to test the methods in a PD population will also run for a shorter duration. The treatment will occur over the course of 10 days rather than 40 to test initial feasibility of the methods in PD. Participants will attend the initial baseline visit in clinic, with the remaining 9 sessions occurring from home with remote supervision.

PD Specific Outcome Measures: Before and after each session, participants will complete brief measures to monitor for any stimulation-related events as well as mood and fatigue. In addition, a pain scale will be administered during the session. Participants will also complete baseline and study-end inventories of mood and fatigue and complete a brief battery of cognitive tests, to help guide power estimates for the future trials. A summary of outcome measures can be found in Table 3.

Test	Screening	Baseline	Daily Study Sessions (2- 10)	End of Study Session	Online/ Telephone Survey (Study end date + 1 month)
Medical Clearance	X				
Expanded Disability Status Scale	X			X	
Wide Range Achievement Test (WRAT-4)	X	X			
Symbol Digit Modalities Test (SDMT)	Х	Х		Х	
Beck Depression Inventory-Fast Screen		Х		X	
tDCS Aptitude Test		Х			
tDCS Tolerance Test (2.0 mA, will possibility to repeat at 1.5 mA)		Х			
Multiple Sclerosis Neuropsychological Questionnaire (MSNQ)		X		Х	Х
PROMIS Measure of Fatigue, Mood and Health-Related Quality of Life		X		X	X
Neuro-Quality of Life		Х		X	Х
Fatigue Impact Scale		X		X	X
Fatigue Severity Scale		Х		Х	Х
Pittsburgh Fatigability Scale		Х		X	

Table 3

Attention Network Test-	Х		Х	
Interaction				
Cogstate Brief Battery	Х		Х	
ERTSLab Processing Battery	Х	X	X	
Controlled Oral Word Association	Х		X	
Rey Auditory Verbal Learning Test	Х		X	X (delayed recall only)
Brief Visuospatial Memory Test- Revised	Х		X	
King Devick Test	Х		X	
Test of Everyday	Х		X	
Cognitive Ability				
Grip Strength	Х		X	
Grooved Pegboard	Х		Х	
Positive and Negative Affect Scale (PANAS)	Х	X	X	
Visual analog scale for fatigue (pre- and post- session)	X	X	X	
Visual analog scale for pain (pre-, early-, mid- and post-session)	Х	X	X	
Tolerability questionnaire - administered by study staff		X		
(pre- and post-session) Safety and tolerability questionnaire –self- report (pre- and post- session)		X		

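### The baseline tolerance test is described with two different sets of current levels: 2.5 mA down to 1.0 mA in the running text of Sections V and VI, and 2.0 mA with a possible repeat at 1.5 mA in Tables 2 and 3

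*Combined protocol and SAP*

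**What the plan says.** The running text gives one version. Section V, under Study Design, states: "Dose will be up to the target of 2.5 mA with reduction to 2.0, 1.5, or 1.0 mA based on tolerability testing at baseline". Section VI, under the aptitude screen and tolerability test, states: "The tolerability test will first take place using 2.5 mA stimulation". It then steps down in decrements of 0.5 mA "till finally a base 1.0 mA stimulation is offered". The same paragraph attaches two consequences to the result. The first concerns dose: "Once the tolerable dose is established, it will remain constant throughout the study". The second concerns eligibility: "If the participant cannot tolerate any of the offered stimulation levels, they are excluded from the study". Specific Aim 1 in Section IV gives 2.5 mA as the upper limit for active stimulation, and the sham description in Section VI gives 2.5 mA as the ramp target.

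The schedules give another version. The row in Table 2 (MS) reads "tDCS Tolerance Test (2.0 mA, will possibility to repeat at 1.5 mA", and the row in Table 3 (Parkinson's disease) has the same wording. Neither row mentions 2.5 mA or 1.0 mA.

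Both versions are in use. For the baseline visit, Section VI says: "Prior to tDCS training, the tests and evaluations detailed in Table 2 will be administered". The tolerance-test row in Table 2 has no asterisk, so it is not among the measures that staff may omit. For the Parkinson's part, Section XI says of its procedures: "Will mirror the exact methods detailed in section" VI, and then supplies Table 3.

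**The concern.** The test decides how much current a participant receives in every later session (40 sessions in MS, 10 in Parkinson's disease) and whether the participant can take part at all. If staff could reasonably take its levels from either of two places, two participants with the same tolerance could be handled differently.

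Three things depend on this: a uniform intervention, a stable definition of who is excluded as intolerant, and the planned description, in the Statistical Analyses of Section XI, of Parkinson's participants who fail the test. The study is also meant to deliver a structured protocol for later trials, and dose setting is one of its central steps.

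**Working it through.** The plan has no stated figure to reproduce, so the check is a comparison of passages followed by a count of cases.

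**Inputs**

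- Levels in the running text (Section V, Study Design; Section VI, tolerability test): 2.5, 2.0, 1.5, 1.0 mA.
- Levels in the schedules (Tables 2 and 3): 2.0 mA, possibly 1.5 mA.
- Dose rule (Section VI): the highest level tolerated becomes the dose and is then held constant.
- Exclusion rule (Section VI): a participant who tolerates none of the levels offered is excluded.

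**Assumptions**

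- The tables contain no dose rule and no exclusion rule. The third column below therefore applies Section VI's rules to the tables' two levels.
- A participant who tolerates one level also tolerates every lower one.
- The repeat at 1.5 mA takes place when 2.0 mA is not tolerated.

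| Highest level tolerated | Running text | Tables' levels with Section VI's rules | Change |
|---|---|---|---|
| 2.5 mA | assigned 2.5 mA | assigned 2.0 mA | dose |
| 2.0 mA | assigned 2.0 mA | assigned 2.0 mA | none |
| 1.5 mA | assigned 1.5 mA | assigned 1.5 mA | none |
| 1.0 mA | assigned 1.0 mA, enrolled | no tolerated level offered, excluded | eligibility |
| none of these | excluded | excluded | none |

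**Results**

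- Two of the five cases change, one in dose and one in eligibility.
- In the first row the dose differs by 2.5 − 2.0 = 0.5 mA. As a ratio, 2.0/2.5 = 0.80, or 20% less, in each session.
- The lowest level offered differs by 1.5 − 1.0 = 0.5 mA. Participants who fail under the tables' levels are all those who fail under the text, plus those who tolerate 1.0 mA but not 1.5 mA. Among the same people tested, the group described as failing in Section XI can therefore only stay the same or grow.
- The number of people in the two affected rows cannot be calculated. The documents report no tolerance rates by level.

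**The case against.** The strongest reply is that the tables are summaries and the levels are only a parenthesis in a row label. The full procedure has its own heading in Section VI, with ramp times, starting level, decrements, dose rule and exclusion rule. Specific Aim 1, Study Design, the sham description and the tolerability paragraph all use 2.5 mA as limit, target or first level. The Parkinson's part mirrors Sections V and VI with named exceptions (open label, shorter duration), and different test levels are not among them. On this view the table rows are probably out of date and staff would rarely act on them.

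Much of this stands. It makes divergent use less likely, and it shows that no single passage prescribes 2.0 mA for someone who tolerates 2.5 mA, or excludes someone who tolerates only 1.0 mA. Both results come from combining the tables' levels with Section VI's rules. The reply does not remove the contradiction, because Section VI refers staff to Table 2 and nothing says that the rows are superseded.

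A reader might infer more than the documents support:

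- **That Table 2's study-end mark for the test conflicts with the text.** It does not. The Study End Visit paragraph has the baseline tests given again, which agrees with the mark. Study Design says that dose reduction rests on baseline testing, not that testing happens only then.
- **That a primary outcome is affected.** Tolerability appears in the statement of purpose but is a secondary outcome in Specific Aim 1, in the Analytic Plan and in the Parkinson's aim. The MS feasibility criterion, completion of 80% of sessions, is defined independently of the test levels.
- **That the randomised comparison is biased.** Nothing ties either version to a particular arm, and Section VI says that procedures are the same in all three conditions.
- **That Section V stands wholly against the tables.** Table 2 is itself in Section V, so that section disagrees with itself.

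**Conclusion.** The contradiction is certain, since it can be read directly from the text. One baseline test has four levels in the running text and two in both schedules, and no rule of precedence is given. It needs correcting because the test determines delivered current and eligibility.

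The consequences are conditional. If Section VI's rules are applied to the tables' levels, the dose is 20% lower for participants who tolerate 2.5 mA, and participants who tolerate 1.0 mA but not 1.5 mA are excluded. Participants whose highest tolerated level is 2.0 or 1.5 mA, and those who tolerate none, are unaffected. The number affected is unknown. Out-of-date table rows are a plausible explanation, but the documents do not say so, and this point takes no view on which version is right.

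**What to change.** Reconcile four places: Study Design in Section V, the tolerance-test row of Table 2, the tolerability test in Section VI, and the tolerance-test row of Table 3. One starting level, one step sequence and one exclusion rule should appear in all of them. The investigator must decide which version is correct. The definition of failing the test in the Statistical Analyses of Section XI then follows from the agreed rule.

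The cost is an editorial amendment to two table rows or to the corresponding text. It needs no additional participants or procedures.

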#### A pilot study of remotely-delivered (tDCS) combined with cognitive training in adults with multiple sclerosis (MS) (S15-01189)

fatigue (pre- and post-								
Visual analog scale for pain (pre-, early-, mid- and post-session)		Х	X	X	X	X		
Tolerability questionnaire - administered by study staff (pre- and post-session)			X		X			
Safety and tolerability questionnaire –self-report (pre- and post-session)			X		X			
Score for Computerized cognitive games (daily)*			Х		Х			
Daily assessment of sleep			Х		X			
Patient and Caregiver Questionnaires*						Х		
Participant Evaluation of Study Procedures*			Х	Х	X	Х		
Count of successful tDCS sessions (confirmation code by session days)			X	X	X	X		
Optional measures that may b	e exclude	d based on s	tudy persor	nel judgem	ent are indicat	ed by an aster	risk.	

# e)Analytic Plan:

Specific Aim 1 is to determine feasibility; to be measured by the number of participants successfully completed using the proposed protocol for training and monitored administration. As would be expected, there is a high rate of compliance for in-clinic tDCS administration and therefore remotely-supervised administration should be designed to be similarly compliant. Study success will be defined by 80% participants having completed 80% sessions, shown to be the target compliance for previous tDCS studies. We will also determine the effectiveness of our sham procedures to ensure blinding, as tested by comparing those who accurately identified the sham condition. We will assess whether the frequency or type of side effects differ between the active and control conditions and whether they occur at the same rate as reported from studies of in-clinic administration. Secondary outcomes will be tolerability, participant-reported adverse events, and comparisons of active and control conditions on these measures.

Specific Aim 2 will be to determine preliminary signals for efficacy, and to have pilot findings to determine necessary sample sizes for an adequately-powered clinical trial. For each participant, change scores will be calculated between baseline and study end scores on measures of fatigue and cognitive functioning. These difference scores will then be described and compared between groups (t-tests and ANOVA related analyses) to determine signals of efficacy for active tDCS paired with cognitive remediation vs. active tDCS paired with non-adaptive puzzle and board games vs. sham tDCS paired with cognitive remediation.

# VI. METHODS AND PROCEDURES

All remotely-supervised sessions will be completed while connected to a video session with the study technician. The protocol is designed to have a decision-tree series of checkpoints that must be met in order to proceed at each step (Figure 2). These checkpoints address compliance (attendance, ability to complete the procedures as instructed, following the study guidelines) and tolerability (at any time, if any predefined events are reported). Following state of the art in tDCS research, devices will be programmed in advance by the PI to provide either active or sham sessions following current standards for blinding. During a sham session, the device is programmed to ramp up to the desired intensity (target 2.5 mA) and ramp down for the initial 60 seconds, with no current delivery during the following 18 minutes of the session, and then current is ramped up and down for 60 seconds at the end of the session. These brief periods of stimulation serve to mimic the effects of a true stimulation session. Both participants and study coordinator (who administers study outcome measures) will be blinded, and will be asked to guess the assigned condition at study end.

The PI will not be blinded to study condition. The PI or an un-blinded study technician will preprogram devices according to randomization and then provide to the study coordinator for each participant. That is, the study coordinator and participant will be blinded to which condition programmed to the assigned device. All procedures will be the same for all three conditions. Adverse events will be addressed in either condition, and the study PI will always know the assigned condition for each participant.

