**c)** Randomization: Participants will be assigned to each condition in a 1:1:1 Stratified randomization procedure. Participants will be matched according to the degree of cognitive impairment (Symbol Digit Modalities test or SDMT score) and neurologic (motor) impairment (Expanded Disability Status Scale or EDSS score). Participants will be randomized to either the active tDCS condition paired with cognitive remediation or one of the two control conditions. The positive control condition will consist of cognitive remediation paired with sham tDCS and the negative control condition will consist of active tDCS with non-adaptive puzzle and board games using block randomization of permuted block sizes 3 and 6, based on our experience in cognitive remediation trials. SDMT performance will be categorized compared to published age-normative means (>0.99 SD, 1 to 2 SD and 2 to 3 SD below mean) and EDSS score will be categorized as mildly or moderately impaired (0 to 3.0 vs. 3.5 to 8.0).

d)*Outcome Measures:* Before and after each session, participants will complete brief measures to monitor for any stimulation-related events as well as mood and fatigue. In addition a pain scale will be administered during the session. Participants will also complete baseline and study-end inventories of mood and fatigue and complete a brief battery of cognitive tests including the Brief International Assessment of Cognition in MS or BICAMS, to help guide power estimates for the future trials. A summary of outcome measures can be found in Table 2.

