# X. SUBJECT RECRUITMENT AND CONSENT/ASSENT

#### Subject Identification, Recruitment and Consent/Assent Method of Subject Identification and Recruitment

The MS Comprehensive Care Center of NYU Langone Medical Center has an extensive recruitment base. Patients will be recruited to participate in studies from all over New York and the other continental United States. Patients who are seen by medical staff at NYU Langone Medical Center, who fit the eligibility criteria, will be referred for the study by the study PI and sub-investigators. All physicians and medical staff at the MS Care Center will be presented with the study description. A patient who is seeing one of these medical staff members as their treating physician will be introduced to the study by that medical staff member. If the patient is interested and agrees, then a member of the study staff will contact them. Once a patient is identified, study staff will meet with the patient or call them to provide additional information regarding study participation. After the patient has reviewed the consent form and asked all questions, and provides consent to participate, the patient will be enrolled in the study.

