#### **Process to Document Consent in Writing**

After review of the consent form and prior to the start of the first session, the PI or one of the coinvestigators will obtain written consent with a signature of the patient on the consent form. All original signed consent forms will be maintained in the study file, separate from the participant data.

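### An unblinded PI who knows every past assignment may also refer and consent MS patients, with blocks of 3 and 6 and no stated concealment of the next assignment

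*Combined protocol and SAP*

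**What the plan says.** **Knowledge of assignments.** Section VI (Methods and Procedures) says the PI is not blinded, that "The PI or an un-blinded study technician will preprogram devices according to randomization", and that "the study PI will always know the assigned condition for each participant". It also describes the PI programming devices ahead of use. The people described as blinded are participants and the study coordinator.

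**Control of entry.** In Section X, suitable MS patients "will be referred for the study by the study PI and sub-investigators". Under Process of Consent, the PI or a trained team member goes through the consent form. Under Process to Document Consent in Writing, "the PI or one of the coinvestigators will obtain written consent".

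**Randomization.** Section V(c) states: "Participants will be assigned to each condition in a 1:1:1 Stratified randomization procedure", "using block randomization of permuted block sizes 3 and 6". The strata come from three bands of SDMT performance and two bands of EDSS score.

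**Order of events.** Under Screening in Section VI, consent is signed at the visit where screening is done, and an MS Center clinician then confirms eligibility. Table 2 lists SDMT and EDSS as screening measures. The aptitude and tolerability tests follow at the baseline visit.

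**Not stated.** The protocol does not say who generates or holds the sequence, when an assignment is released relative to consent and eligibility, or how the next assignment is kept from those who enroll.

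**The concern.** Concealing the next assignment until a patient is irrevocably entered is what stops the arms from being filled selectively. Here one role may hold knowledge of all earlier assignments and also have a hand in who enters and when. Small blocks within strata turn a known history into information about the next assignment.

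Entry leaves room for discretion. Some criteria in Section VII are judgments, such as whether deficits or a psychiatric disorder would interfere with participation, and the timing of referral and consent is open. Someone expecting a particular arm could, without intending to, bring a more motivated or less fatigued patient forward or hold one back. Blinding participants and the coordinator afterwards does not undo that.

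The exposed results are the comparison of completion between conditions (Section IX, Aim 1) and of change in fatigue and cognition (Sections V(e) and IX, Aim 2). Aim 2 is planned as t-tests and ANOVA-type analyses of change scores, with no covariate adjustment specified. Stratification balances SDMT and EDSS bands but not motivation or baseline fatigue.

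**Working it through.** The plan gives no figure for predictability, so there is none to reproduce. The question is how often someone who knows the past assignments would guess the next arm correctly.

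**Inputs from the protocol**
- Three arms, 1:1:1, so chance is 1/3 = 33.3% (Section V(c)).
- Block sizes 3 and 6 (Section V(c)).
- 3 SDMT bands × 2 EDSS bands = 6 strata (Section V(c)).
- 85 MS participants (Section IV), so 85/6 ≈ 14 per stratum if evenly spread.

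**Assumptions not in the protocol**
- Each block is size 3 or 6 with probability one half.
- Strata are evenly filled, unless stated otherwise.
- The guesser always picks the most probable arm.

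**1. Block size known (exact).** With r_i places left for arm i, the best guess is right with probability max(r_i)/Σr_i.
- Block of 3: the successive probabilities are 1/3, 1/2 and 1. The mean is (11/6)/3 = 61.1%, and one assignment in three is certain.
- Block of 6: the expected values are 1/3, 2/5, 1/2, 8/15, 3/5 and 1. They sum to 101/30, and 101/30 ÷ 6 = 56.1%. The last place is always certain and the fifth is certain with probability 1/5, so 1.2/6 = 20.0% are certain.
- Equal mix of blocks: (3 × 61.1% + 6 × 56.1%)/9 = 57.8% correct, and (3 × 33.3% + 6 × 20.0%)/9 = 24.4% certain.

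**2. Stratum known, current block size unknown.** The guesser knows the history in the stratum and that sizes are 3 or 6. The probability of arm i is Σ w × r_i/Σr over the possible block states, with weights w updated by Bayes' rule after each assignment. Results from 6,000 simulated strata for each size:

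| Participants in stratum | Correct guess | Certain |
|---|---|---|
| 7 | 54% | 6% |
| 14 | 55% | 7% |
| 28 | 57% | 8% |

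Simulating all 85 participants over six strata gives 56% correct and 7% certain.

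**3. Stratum not yet known.** This is the position at consent, which precedes SDMT and EDSS screening. The probability of arm i is now averaged over strata, Σ π_s × p_s(i), where π_s is the share of patients in stratum s. The guess is correct about 44% of the time with even strata and about 47% under one assumed uneven spread. No assignment is certain. The more patients are concentrated in one stratum, the closer this comes to the figure in step 2.

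**The case against.** The strongest reply is that the protocol is silent on concealment but does not describe a PI who controls entry.

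- **Timing.** Consent comes before the screening that defines the stratum. When the PI refers or consents, the 55–57% figure applies only if the stratum is already known, for example from clinic records, and the documents do not address that. This stands, and it is why 44–47% is reported alongside.
- **Other gatekeepers.** An MS Center clinician confirms eligibility, the study physician gives medical clearance, and the technician judges aptitude and runs the tolerability test. These roles dilute the PI's control. None is stated to be independent of the PI or unaware of past assignments.
- **Alternative wording.** The PI is one of several people who may program devices, review consent or obtain the signature, and treating physicians and study staff also bring patients in. The exposure therefore arises only when the PI takes part.
- **The list.** A reader might infer that a PI who programs devices can see every upcoming arm. The text does not support this. It nowhere says the PI holds the list, and it is compatible with one assignment being released per enrolled participant. Device programming alone separates only active from sham, and two of the three arms are active.
- **Consequence.** A reader might also infer that the feasibility result is biased. The criterion in Section V(e), that 80% of participants complete 80% of sessions, is stated overall. Steering patients between arms does not by itself move it.

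These points reduce the size and reach of the problem. They do not supply a safeguard: the protocol assigns both kinds of duty to the same role and describes nothing that keeps them apart.

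**Conclusion.** The point holds as a weakness in how duties are allocated, not as evidence that entry was or will be manipulated. When the PI takes part in entering an MS patient, the next arm can be guessed about 44–47% of the time before the stratum is known and about 55–57% after, against 33% by chance. About 7% of assignments are certain in the second case. Assignments could be known outright only if the PI sees the list, which the documents do not say.

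The figures rest on an equal mix of block sizes and on assumed stratum shares. They describe predictability; they have not been converted into bias on any outcome, and the documents give no basis for doing so. The between-arm comparisons in Aims 1 and 2 could be biased. The overall 80%/80% criterion and the open-label, single-arm Parkinson's cohort are not directly affected. No sample size or power figure changes. The correction is worth making because the study is meant to set the procedures for later controlled trials.

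**What to change.** 1. **Section VI:** give the allocation list and all device programming to the un-blinded technician only, with no part in referral, eligibility or consent. Another staff member must then run the baseline aptitude and tolerability tests, since they decide entry.
2. **Section X:** for the randomized MS cohort, remove the PI from referral, entry decisions and consent. Use co-investigators or team members who are not told past assignments or block sizes.
3. **Section V(c):** move the block sizes to a document that enrolling staff do not see.
4. **Sections V(c) and VI:** state that each assignment is released only after consent and every eligibility check, including the baseline aptitude and tolerability tests, are complete and recorded.

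The PI may still learn each condition once it is assigned, so the statement in Section VI that the PI knows every participant's condition, made alongside adverse-event handling, can stay.

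**Cost.** No extra patients are needed, and the duties move between roles the protocol already names. The PI can no longer personally refer or consent MS participants. Co-investigators who take over those tasks must not be shown assignments at the weekly meetings described under Monitoring in Section IX. If the first session is held at the baseline visit, the un-blinded technician has to be available that day to program the device.
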